3.1. Description of the Study Population

Inclusion Criteria: Patients are eligible if, at the time of index angiography, they have underlying chronic kidney disease (CKD) with estimated glomerular filtration rate (eGFR) values calculated using the 4-variable Modification of Diet in Renal Disease (MDRD) formula as described on page 33 of the protocol:

- (1) eGFR <60 ml/min/1.73 m² and a diagnosis of diabetes mellitus, or
- (2) eGFR <45 ml/min/1.73 m² regardless of whether or not they have diabetes mellitus.

Table 2. Exclusion Criteria. Patients are excluded if they satisfy any of these 13 conditions.

(1) <18 years of age	(8) have de-compensated heart failure
(2) pregnant	(9) having an emergent angiogram
(3) unwilling to comply with 4 and 90 day outcome assessment	(10) received iodinated contrast within past 7 days
(4) participating in a clinical trial	(11) received NAC within past 48 hours
(5) received dialysis	(12) have known allergy to NAC
(6) have stage 5 CKD	(13) have known allergy to iodinated contrast
(7) have unstable baseline Serum Creatinine (SCr)	

3.2. Description of the Intervention Strategy

Eligible patients who consent to participate will be randomized prior to angiography to receive one of 4 regimens: 1) NAC and Bicarb, 2) NAC and Saline, 3) Placebo and Bicarb, or 4) Placebo and Saline. Study drug administration schedule is outlined in Table 3.

Table 3. Study Drug Administration Schedule.

Time	IV	ORAL
Immediately prior to the angiographic procedure	3 to 12 mL/kg of the IV isotonic study crystalloid solution (Bicarb or saline) infused over a minimum of 1 hour and maximum of 12 hours at an infusion rate of not less than 1 mL/kg per hour and not more than 3 mL/kg per hour	NAC or Placebo in an oral dose of 1200 mg (4 capsules) administered within 1 hour preceding the procedure
During the procedure	IV isotonic study crystalloid solution infused at a rate of 1 to 1.5 mL/kg per hour	None
Following the procedure	6 to 12 mL/kg of the IV isotonic study crystalloid solution infused over a minimum of 4 hours and maximum of 12 hours at an infusion rate of not less than 1 mL/kg per hour and not more than 1.5 mL/kg per hour	NAC or Placebo in an oral dose of 1200 mg (4 capsules) administered within 1 hour following the procedure
Day 1 through 4 post procedure	None	NAC or Placebo administered in an oral dose of 1200 mg (4 capsules) twice daily

3.3. Definition of Intention to Treat Sample

All consented and randomized subjects will be accounted for and reported in the CONSORT diagram for the study, however, only those randomized subjects who initiated either IV or oral intervention (i.e., did not drop out or withdraw prior to start of the allocated intervention), will be considered as an intention to treat (ITT) subject to be included in the Data Monitoring Committee (DMC) reports and primary efficacy analysis.

An analytic sample file consisting of only the “ITT” subjects as defined above will be created and maintained throughout the study. This file will be called the “CSP578_ITT” file.

3.4. Definition of per-Protocol sample

Adherence to allocated intervention according to the protocol, as outlined in Table 3, will be ascertained for randomized subjects for identification of “per-Protocol” sub-group. Percent adherence will be determined for IV fluid and oral interventions separately.

Oral medication adherence will be computed by capsule count only as follows:

$$\% \text{ adherence} = \frac{\text{Total\#capsulesTaken}}{40} \times 100\%$$

Those who had (>=80% and <=120%) adherence by the capsule count will be considered as adherent to the protocol.

IV fluid adherence will be based on the recommended ranges for each period (pre-procedure, intra-procedure, and post-procedure) described in Table 3.

Pre – procedure: Volume of 3 to 12 ml/kg

Intra – procedure: Rate of 1 to 1.5 ml/kg/hour

Post – procedure: Volume of 6 to 12 ml/kg

% adherence will be computed as a range from % of lower limit to % of upper limit outlined in Table 4.

Table 4. IV fluid adherence table

Pre-Procedure		Intra-procedure		Post-procedure	
Volume (mL/kg)	% Dose Given	Rate (mL/kg/Hr)	% Dose Given	Volume (ml/kg)	% Dose Given
1	33.3%	0.5	50%	1	16.7%
2	66.7%	0.6	60%	2	33.3%
3	100%	0.7	70%	3	50%
4	100%	0.8	80%	4	66.7%
5	100%	0.9	90%	5	83.3%
6	100%	1.0	100%	6	100%
7	100%	1.1	100%	7	100%
8	100%	1.2	100%	8	100%
9	100%	1.3	100%	9	100%
10	100%	1.4	100%	10	100%
11	100%	1.5	100%	11	100%

12	100%	1.6	106.7%	12	100%
13	108.3%	1.7	113.3%	13	108.3%
14	116.7%	1.8	120%	14	116.7%
15	125%	1.9	126.7%	15	125%

Those who had (>=80% and <=120%) adherence for, at minimum, the pre-procedure and intra procedure periods will be considered as adherent to the protocol.

Those who are adherent to the protocol for both oral study medication and IV study fluid will be included in the “per-Protocol” analytic sub-sample.

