## **C. Blinding**

Providers performing angiography, participating patients, personnel at the study chairmen's office, and research personnel at each site will be blinded to treatment assignment. Study IV

fluids will be provided in coded bags without specific labeling on the bag regarding the composition of the fluid. The appearance of the sodium bicarbonate solutions and sodium chloride solutions will be identical. NAC will be provided as 300 mg capsules or matching placebo capsules prepared by the VA CSP Clinical Research Pharmacy Coordinating Center in Albuquerque, NM. The use of NAC powder as a capsule avoids the difficulty of masking the strong odor and unpleasant taste associated with the liquid formulation of NAC.

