##### 1. IV fluids

We will administer  $\geq 3$  mL/kg of study IV fluid over  $\geq 1$  hour at an infusion rate of not less than 1 mL/kg per hour and not more than 3 mL/kg per hour immediately prior to the angiographic procedure, 1-1.5 mL/kg of study IV fluid per hour during angiography, and  $\geq 6$  mL/kg of study IV fluid over  $\geq 2$  hours following the procedure at an infusion rate of not less than 1 mL/kg per hour and not more than 3 mL/kg per hour. Providers will retain discretion to administer larger volumes of the randomly allocated study IV fluid (up to a maximum of 12 mL/kg) over durations of up to 12 hours pre and 12 hours post-procedure. The protocol will prohibit the delivery of smaller volumes of study IV fluid over shorter durations than the pre-specified minimums described above. In patients who are obese (BMI  $>30$  kg/m^2) and weigh more than 125 kg, calculated rates of fluid administration should be capped based on a weight of 125 kg.

We chose this individualized approach rather than a strict protocol for IV fluid administration for two reasons. First, the optimal rate, duration, and volume of IV fluid for the prevention of CIAKI and other adverse outcomes have not been conclusively determined. Although there is a general belief that “more fluid” is superior to “less fluid,” this premise has not been rigorously tested. This uncertainty is underscored by published expert recommendations for the use of IV fluids that acknowledge the lack of evidence to support a specific IV fluid regimen. Second, requiring that IV fluids be administered at a specific rate for a precise period of time would likely be perceived as non-evidence based, could significantly limit provider willingness to have

their patients participate, and would reduce the generalizability of study findings. In clinical practice, the volume and duration of pre and post-procedure IV fluid often vary based on the clinical setting and individual patient circumstances.

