## 2. NAC and placebo

NAC or placebo will be administered at a dose of 1200 mg orally to all patients approximately 1 hour prior to angiography, approximately 1 hour following the procedure, and then twice daily for the next 4 days. Although initial studies using NAC utilized a dose of 600 mg per dose, subsequent studies have suggested greater benefit with higher doses of this agent. Therefore, we will provide 1200 mg per dose of oral NAC. Nearly all prior studies administered NAC for a total of 2 days. However, iodinated contrast may persist in the kidney tubules for a prolonged period of time, particularly in patients with decreased kidney function. Although it is not known whether this residual contrast results in persistent renal damage, there may be benefit to more sustained therapy with NAC with little added cost or risk. Therefore, we will administer NAC capsules twice daily for 5 days.

Although several prior trials investigated the benefit of NAC administered intravenously for the prevention of CIAKI, we chose to use oral administration for three reasons. First, oral NAC is associated with minimal risk, while up to 15% of patients who receive IV NAC experience an adverse reaction, which rarely, includes anaphylaxis. Second, IV NAC is considerably more expensive than the oral preparation. Finally, there is no clear evidence that

IV NAC offers greater protection against CIAKI or serious adverse outcomes compared to oral NAC.

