#### **E. Additional exploratory analyses**

We will explore several other hypotheses related to the binary 90 day MAKE-D outcome:

1. The combination of bicarbonate and NAC (interaction term) is more effective than bicarbonate or NAC alone.
2. (Per Protocol analysis) Bicarbonate, NAC, and their combination reduce the incidence of the primary outcome, MAKE-D, among subjects who received the full dose of bicarbonate.
3. (Per Protocol analysis) Bicarbonate, NAC, and their combination reduce the incidence of the primary outcome, MAKE-D, among subjects who received the full course of NAC.
4. Bicarbonate, NAC, and their combination reduce the incidence of the individual components of MAKE-D, each treated as a separate outcome: death, need for acute dialysis, and persistent decline in kidney function.
5. Bicarbonate, NAC, and their combination reduce the incidence of each of the individual cardiovascular components of the secondary outcome; namely acute coronary syndrome, heart failure, and cerebrovascular accident.
6. Bicarbonate, NAC, and their combination result in a greater reduction in the incidence of MAKE-D outcomes in subjects who develop CIAKI compared to those who do not develop CIAKI.
7. Bicarbonate, NAC, and their combination increase the mean number of days that participants are alive and hospitalization free (hospital free days) in the 90 days after angiography.

8. The benefits of bicarbonate, NAC, and their combination on MAKE-D outcomes are independent of the volume and rate of fluid administration above the minimum values prescribed in the protocol.

This brief list entails a large number of analyses. However, the sample size is large and the implicit hypotheses are highly inter-correlated. Thus, we anticipate that we can use a significance level of 1% ( $p = 0.01$ ) to detect associations of potential clinical importance in these exploratory analyses.

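### The fixed 40-capsule denominator in SAP 3.4 removes fully compliant patients who die early, together with their endpoint event, from both per-protocol analyses

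*SAP*

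**What the plan says.** SAP 3.4 sets the oral rule: "Oral medication adherence will be computed by capsule count only as follows", followed by a ratio of total capsules taken to 40. It continues: "Those who had (>=80% and <=120%) adherence by the capsule count will be considered as adherent to the protocol". No provision is made for a patient who dies, or has another endpoint event, during the five-day course.

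For fluid, SAP 3.4 lists reference ranges for three periods, including "Post – procedure: Volume of 6 to 12 ml/kg". The classification asks for less: those with 80–120% "adherence for, at minimum, the pre-procedure and intra procedure periods will be considered as adherent to the protocol". A patient must satisfy both the oral and the fluid criterion to enter the per-protocol set.

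The set is used in two of the five scenarios in SAP 5.3.5. Scenario (1) applies the 80–120% window. Scenario (2) keeps the 80% floor and drops the ceiling. Death is a component of the primary endpoint (SAP 3.5.1).

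Protocol XVII.E describes its per-protocol analyses as exploratory and lists fluid and NAC separately. The fluid analysis is "among subjects who received the full dose of bicarbonate". Protocol VII.D.1 adds that, in obese patients above 125 kg, "calculated rates of fluid administration should be capped based on a weight of 125 kg". The SAP does not mention this cap.

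**The concern.** A per-protocol set is meant to select on what the patient did with the assigned treatment. With a denominator of 40 for everyone, it also selects on survival to the evening of day 3, because no one who dies sooner can reach 32 capsules however compliant they were. Every such exclusion takes out a primary-endpoint event.

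Because oral and fluid adherence are both required, the patient also leaves the bicarbonate comparison, even after a complete infusion. If a per-protocol estimate then differed from the ITT estimate, part of the difference could come from this exclusion and not from adherence.

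**Working it through.** **Inputs**

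- Capsule strength, Protocol VII.C: "NAC will be provided as 300 mg capsules or matching placebo capsules".
- Schedule, Protocol VII.D.2: 1200 mg about 1 hour before the procedure, then "approximately 1 hour following the procedure, and then twice daily for the next 4 days". SAP Table 3 gives the same number of doses.
- Window, SAP 3.4: 80–120% of 40 capsules.
- Planning rates, Protocol XVII.A.2 and SAP section 4: 1% deaths at 90 days in the database cohort; 7.6% overall MAKE-D; N = 7,680.

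**Reproducing the plan's figures**

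- Doses: 2 on day 0 + 2 × 4 = 10. Capsules per dose: 1200/300 = 4. Total: 10 × 4 = 40, as in the SAP.
- Window in capsules: 0.80 × 40 = 32 to 1.20 × 40 = 48.
- The fluid percentages in SAP 3.4, Table 4 also reproduce as volume or rate divided by the lower limit below the range, 100% within it, and divided by the upper limit above it.

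**Highest possible score by time of death, with every scheduled dose taken**

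| Last dose taken | Capsules | Score on 40 | Score on capsules due |
|---|---|---|---|
| End of day 0 | 8 | 20% | 100% |
| End of day 1 | 16 | 40% | 100% |
| End of day 2 | 24 | 60% | 100% |
| First dose, day 3 | 28 | 70% | 100% |
| Second dose, day 3 | 32 | 80% | 100% |

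The first point at which a perfectly compliant patient can qualify is the second dose on day 3. Scenario (2) changes only the upper limit, so it restores none of the patients above that row.

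**Size**

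The documents do not say when deaths occur within the 90 days, so the fraction in the window is an assumption.

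- Deaths: 0.01 × 7,680 = 77. Events: 0.076 × 7,680 = 584.
- If 5% fall in the window: 76.8 × 0.05 = 3.8 patients; 3.8/584 = 0.7%.
- If 20% fall in the window: 76.8 × 0.20 = 15.4 patients; 15.4/584 = 2.6%.
- Reference points: an even spread over 90 days (4/90) gives 3.4 patients, 0.6%; a heavier early share of 30% gives 23 patients, 3.9%.

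The 1% comes from a cohort whose overall rate was 8.7%. On that base (0.087 × 7,680 = 668 events), 3.8 to 15.4 patients are 0.6–2.3%, so the choice of base matters little.

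**Clarification: dosing weight**

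The minimum pre-procedure volume under the cap is 3 × 125 = 375 mL. If mL/kg were computed on actual weight, the score would be 375/(3 × 150) = 83.3% at 150 kg and 375/(3 × 160) = 78.1% at 160 kg. It crosses 80% at 125/0.80 = 156.25 kg. On the capped weight it is 100% throughout.

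**Clarification: fluid criterion**

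A patient given 3 mL/kg before the procedure and none after it can qualify. That is 3/(3 + 6) = 33% of the combined pre- and post-procedure minimum.

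**The case against.** The strongest reply is that nothing confirmatory is touched. SAP 5.3 runs the primary analysis on the ITT sample, scenarios (3) to (5) of SAP 5.3.5 also use ITT, and the protocol calls its per-protocol analyses exploratory. No primary test, alpha or power figure changes. This stands, and it limits the point to a minor correction.

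A reader might infer that everyone who stops capsules early is misclassified. That does not follow. A patient who stops for other reasons did not take the course, and leaving such patients out is what a per-protocol set does. Exclusion becomes outcome-dependent only through death or through a stop caused by the endpoint event itself.

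A reader might also add the 5% of patients starting dialysis to the 1% who die. On the same 5–20% timing, that gives 7,680 × 0.06 × 0.05 to 0.20 = 23–92 patients, or 4–16% of events. The documents do not support this. Nothing says that starting dialysis ends capsule intake: Protocol VII.F tells participants to bring study medication if hospitalized, and VII.H.4 has in-hospital administration recorded. Protocol XVII.A.2 also notes that the component events overlap, so the two rates cannot simply be summed.

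A third inference is that the fluid rule wrongly counts patients without post-procedure fluid as adherent. The SAP's List of Revisions, item 2, shows that the rule was chosen deliberately. It is also consistent with Protocol VIII.C.2, which foresees post-procedure fluid being stopped for complications. Requiring that volume would exclude patients because of a prognostic event after randomization, which is the same kind of selection as in the oral rule. What remains is a mismatch with the protocol's full-dose wording, a term that the protocol does not define for this analysis.

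Finally, the 125 kg cap cannot be said to be ignored. SAP 3.4 measures adherence against the protocol, which contains the cap, so dosing weight is as natural a reading as actual weight. The weight is simply not stated.

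**Conclusion.** The point holds for early deaths. The denominator in SAP 3.4 makes it impossible for a compliant patient who dies before the second day-3 dose to be per-protocol, so scenarios (1) and (2) condition on a component of the primary endpoint. The mechanism follows directly from the stated rule; only its size is uncertain. With 5–20% of the planned deaths in the window, it is about 4–15 patients, or 0.7–2.6% of roughly 584 events. That rests on the 1% planning death rate and on assumed timing. The documents do not show whether these deaths would be unequal between arms, so no direction of bias can be stated.

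The dosing-weight and full-dose matters are requests for clarification. The first could change a patient's status only if actual weight is used, only above 156.25 kg, and only for dosing near the minimum; the documents give no weight distribution. The second concerns how the set is described. The pre- and intra-procedure criterion is not an error.

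**What to change.** In SAP 3.4, replace the fixed 40 by the number of capsules due up to death, or up to a documented stop caused by an endpoint event, for patients to whom that applies. Keep 40 for all others. The denominator should not be cut at withdrawal in general, because someone who withdraws after one dose would then score 100%. State how a patient is classified if no capsule had yet fallen due.

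In the same section, add one sentence saying that mL/kg adherence uses the protocol's dosing weight, capped at 125 kg where the cap applies. Reconcile the fluid criterion with Protocol XVII.E by naming the set for what it measures, namely pre- and intra-procedure fluid adherence. A set requiring all three periods could be reported beside it under its own label. It would be smaller and would need a note that fluid stopped for complications affects membership.

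The cost is SAP wording and one derived variable, built from dates of death and endpoint events and from the capsule records that the protocol already collects. No data collection, treatment rule or primary analysis changes.

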3.5. Description of the Efficacy Endpoints

3.5.1. Primary Endpoints

The primary endpoint for the study is the composite end-point assessed at 90 days post index angiographic procedure and is comprised of the 3 events described below. Those subjects with at least one of these 3 events will be considered to have the primary study endpoint.

(1) Death from all causes to be verified by medical record and/or vital status registry documentation such as the VA Beneficiary Identification and Records Locator System, the National Center for Health Statistics National Death Index database, the Social Security Administration’s Death Master File.

(2) Acute dialysis defined as the initiation of any modality of renal replacement therapy, which includes intermittent hemodialysis, peritoneal dialysis, continuous renal replacement therapy, or prolonged intermittent renal replacement therapy.

(3) Persistent decline in kidney function defined as ≥50% increase in SCr at 90 days post procedure relative to baseline SCr collected pre-Angiography procedure, and derived as follows.

$$(SCr_{day90} / SCr_{pre-procedure}) * 100\% \geq 150\%$$

Both the initial 90 day specimen and the confirmatory sample processed at the Central Lab must establish a ≥50% increase in SCr to qualify as an endpoint event.

Please note:

1. 90 day blood sample is allowed to be collected within 6month window starting 90 days post index angiographic procedure.
2. 90 day blood sample is not necessary if pt is already on dialysis at day 90 post index angiographic procedure.

3.5.2. Secondary Endpoints

The secondary endpoints **except for CIAKI** for the study are assessed at 90 days post index procedure and they include the following individual outcomes:

(1) CIAKI defined by an increase in SCr of ≥ 0.5 mg/dL and/or $\geq 25\%$ increase at 96 hours following contrast administration, derived as follows.

$$(\text{SCr}_{96\text{Hours}} / \text{Scr pre-procedure}) * 100\% \geq 125\%$$

(2) Death from all causes to be verified by medical record and/or vital status registry documentation such as the VA Beneficiary Identification and Records Locator System, the National Center for Health Statistics National Death Index database, the Social Security Administration's Death master File.

(3) MAKE defined by (a) initiation of any modality of renal replacement therapy, which include intermittent hemodialysis, peritoneal dialysis, continuous renal replacement therapy, or prolonged intermittent renal replacement therapy, or (b) persistent decline in kidney function as defined in **3.5.1**.

(4) Hospitalization with acute coronary syndrome, heart failure, or cerebrovascular accident within 90 days following the index angiographic procedure. These outcomes will be defined as a primary or secondary discharge diagnosis of acute coronary syndrome (i.e., STEMI, NSTEMI, unstable angina), heart failure, or cerebrovascular accident documented in the VA electronic medical record or the hospital discharge summary obtained for non-VA hospitalizations. Note: This will include the occurrence of any of these events during the index hospitalization.

(5) All-cause re-hospitalization within 90 days of the index angiographic procedure assessed as episodes of re-hospitalization, days of hospitalization (inclusive of the index hospitalization), and hospital free days (alive and not in the hospital) through day 90.

